1 SYNOPSIS

Study Acronym	LYMA101
Title	Phase II study to evaluate the efficacy of upfront obinutuzumab in mantle cell lymphoma patients treated by DHAP followed by autologous transplantation plus obinutuzumab maintenance then MRD driven maintenance
Study Product	IMP: obinutuzumab
Protocol version	5.0 – 04/04/2018
EudraCT N°	2016-000548-33
Sponsor	LYSARC
Coordinator Investigators	Prof. [name] Prof. [name]
Anticipated Countries	France
Objectives	
The Primary objective is to evaluate the efficacy of upfront Obinutuzumab (GA101) at the molecular level (MRD) in bone marrow after induction, after the 4 cycles or at premature discontinuation, in patients with previously untreated MCL treated by DHAP.
 
Secondary objectives are:
 
 • To evaluate the efficacy of the obinutuzumab in patients with MCL treated by DHAP before ASCT, after ASCT and every 6 months in terms of clinical response (Cheson 99) and MRD plus in terms of FDG-PET before and after ASCT • To evaluate PFS, Overall survival at study end • To evaluate the incidence of stem cell collection failure after obinutuzumab-DHAP = GA-DHAP • To evaluate MRD negativity after 3 years of maintenance and maintenance “on-demand” • To evaluate PET results after 3 years of maintenance • Duration of MRD negativity • To evaluate tolerability of obinutuzumab at induction and then “on-demand” 
Exploratory objective is :
 
 • To determine baseline prognostic factors on PFS and OS.

Inclusion Criteria	
 • Age ≥ 18 and age ≤ 65 • Histologically confirmed (according to the WHO classification) mantle cell lymphoma. The diagnosis has to be confirmed by phenotypic expression of CD5, CD20 and cyclin D1 or the t(11;14) translocation. • Bone marrow aspiration performed at inclusion for MRD analyses • Eligible for autologous stem cell transplant • Previously untreated MCL • Stage Ann Arbor II-IV in need of treatment • ECOG performance status of 0 – 2 • Life expectancy of more than 3 months • Written informed consent • Patient affiliated by any social security system
Exclusion Criteria	
 • Severe cardiac disease: NYHA grade 3-4 • Impaired liver (ALAT/ASAT ≥ 2.5ULN, bilirubin ≥ 1.5ULN), renal (calculated creatinine clearance < 50ml/min) or other organ function which will interfere with the treatment, if not related to lymphoma. • History of chronic liver disease • Hepatic veno-occlusive disease or sinusoidal obstruction syndrome • Any of the following laboratory abnormalities, if not result of a BM infiltration: 
 - Absolute neutrophils count (ANC) $<1,500 /mm^3$ ($1.5 \times 10^9/L$) - Platelet counts $< 75,000/mm^3$ ($75 \times 10^9/L$) • Pregnancy/Nursing mothers • Fertile men or women of childbearing potential unless: 
 - surgically sterile or ≥ 2 years after the onset of menopause - willing to use a highly effective contraceptive method (Pearl Index <1) such as oral contraceptives, intrauterine device, sexual abstinence or barrier method of contraception in conjunction with spermicidal jelly during study treatment and in female patients for 18 months after end of antibody treatment and in male for the duration of the treatment and after the last dose administered in accordance with the SmpC of the different products administered • Patients with a malignancy that has been treated but not with curative intent, unless the malignancy has been in remission without treatment for ≥ 5 years prior to enrollment. Patients with a history of curatively treated basal or squamous cell carcinoma or melanoma of the skin or in situ carcinoma of the cervix are eligible. • Known seropositivity for HIV, HCV or other active infection uncontrolled by treatment.

	
 Viral infection with hepatitis B virus (HBV) defined as hepatitis B surface antigen (HBsAg) positive and/or Hepatitis B core antibody (anti-HBc) positive Note: Patients who are immune due to hepatitis B vaccination or natural infection (HBs Ag and anti-HBc negative, anti-HBs positive) are eligible. But the patients who are immune due to hepatitis B natural infection should consult liver disease experts before start of treatment and should be monitored and managed following local medical standards to prevent hepatitis reactivation Prior history of Progressive Multifocal Leukoencephalopathy (PML) Vaccination with a live vaccine a minimum of 28 days prior to inclusion (Prolonged B cell depletion) History of severe allergic or anaphylactic reactions to humanized or murine monoclonal antibodies. Known sensitivity or allergy to murine products Psychiatric illness or condition which could interfere with their ability to understand the requirements of the study. Person deprived of his/her liberty by a judicial or administrative decision Person hospitalized without consent Adult person under legal protection
Study design	
Induction
 
GA-BEAM + ASCT → GA101 every 2 months
 
3w 3w 3w 4w/8w
 
● GA101
 
↓ D1 DHAP (or C according to local investigator choice)
 
Maintenance during 3 years
 
GA101 every 2 months
 
Maintenance "on-demand" during 3 years
 
No treatment
 
MRD
 
GA101 every month
 
MRD

Study treatment	
Patients will receive 4 cycles of GA-DHAP* every 21 days followed by ASCT using a GA-BEAM conditioning regimen plus a Obinutuzumab maintenance for 3 years then a Obinutuzumab maintenance on demand according to MRD status. Stem cells will be collected after cycle 3 and/or 4 of GA-DHAP*.
 
Patients with high tumor load may receive a pre-phase treatment of COP. The pre-phase therapy should be started after inclusion and after samples for MRD analysis and cycle 1 of GA-DHAP has to be started 1 week after the end of the COP.
 
In this trial, obinutuzumab is considered as investigational medical product (IMP).
 
Cycle 1 :
 
 Patients will receive their first obinutuzumab infusion (1000 mg) on Day 1 (Cycle 1 Day 1) along with standard premedication. During Cycle 1, obinutuzumab will also be administered on Days 8 and 15.

- Following obinutuzumab infusion, patients will receive DHAP chemotherapy as per standard administration procedures, along with standard premedications.
- Patients will be monitored for signs of acute TLS

Chemotherapy regimen	Dose	D1	D2	D3	D4	D8	D15
Dexamethasone	40mg	X	X	X	X		
GA-101 IV	1000mg	X				X	X
Aracytine IV	2 g/m ² /12h	XX					
Cisplatinum* IV	100 mg/m ²	X					

Cycle 2 to 4: one cycle every 21 days

Chemotherapy regimen	Dose	D1	D2	D3	D4
Dexamethasone	40mg	X	X	X	X
GA-101 IV	1000mg	X			
Aracytine IV	2 g/m ² /12h	XX			
Cisplatinum* IV	100 mg/m ²	X			

G-CSF administration is required during treatment cycles, stem cell collection and ASCT.

*In case of toxicities related to cisplatinum or according to the local investigator choice, Carboplatinum AUC = 5 could be used instead of cisplatinum

ASCT :

GA-BEAM: 4 to 8 weeks after D1 C4

Chemotherapy Regimen GA-BEAM	Dose	D-8	D-7	D-6	D-5	D-4	D-3	D-2	D-1	D0
GA-101 IV	1000mg	X								G
BCNU	300 mg/m ²		X							R
Etoposide	400 mg/m ²			X	X	X	X			A
Aracytine (Cl)	400 mg/m ²			X	X	X	X			F
Melphalan	140 mg/m ²							X		T

Maintenance:

Obinutuzumab maintenance: start between 2 to 3 months after D1 of ASCT. All patients in complete remission, complete remission unconfirmed, partial remission or stable disease (according to Cheson 99) will receive one injection of Obinutuzumab

every 2 months for 3 years.

Treatment	Dose	D1 every 2 months
GA-101 IV	1000mg	X

When the MRD is informative at baseline in bone marrow and/or blood (prior to any treatment, before starting induction), this period will be followed by a maintenance “on-demand” for 3 years only for MRD positive patients at the end of the first 3 years of maintenance, MRD negative patients will stop obinutuzumab infusion. The therapeutic scheme will be one injection every month of Obinutuzumab (one injection at D1, 8 and 15 for the first month and then one time every month) until MRD negativity plus one additional injection after the last MRD negative control. MRD analyses will be continued for all patients with informative MRD and every patient once again with a positive MRD will restart Obinutuzumab maintenance.

treatment	Dose	1 st month			Every month
		D1	D8	D15	D1
GA-101 IV	1000mg	X	X	X	X

This scheme has to be used several times until clinical progression, toxicities or until end of the 3-years period, whichever comes first.

Patients who withdraw from the study treatment or patients who progress will be followed until the end of the trial.

Tests performed at Study

Commencement and follow-up

Commencement:

- Clinical examination and complete medical history
- Full blood count, biochemistry (creatinine, creatinine clearance according to Cockroft-Gault, bilirubin, ALAT, ASAT, albumin, LDH)
- Surgical biopsy (avoid needle biopsies if possible to secure enough material) of tumour tissue for morphology and immunochemistry, frozen tissue if possible
- Bone marrow biopsy/aspiration
- CT-scan of neck, thorax and abdomen/pelvis
- FDG-PET pre-treatment
- gastroscopy/colonoscopy and other examinations if clinically indicated

Evaluation during treatment:

- Clinical exam and biochemistry: D-1 or D1 of each cycle of GA-DHAP, After induction (before ASCT), after ASCT and every two months during 3 years

	
and then every 3 months for 3 years for MRD negative patients and every month for MRD positive patients
 
 • full blood count : before each Obinutuzumab injection (induction, conditioning regimen and maintenance) • CT-scan of thorax and abdomen/pelvis: After induction (before ASCT), after ASCT, every 6 months during the 3 years of obinutuzumab maintenance then every year during the maintenance “on-demand” • FDG-PET: After induction (before ASCT), after ASCT and after 3 years of maintenance • Bone marrow biopsy/aspiration: After induction (before ASCT), after ASCT (before maintenance) if clinically indicated 
MRD monitoring:
 
 • At baseline: blood and bone marrow (BM) aspiration • After induction: blood and BM aspiration • After ASCT: blood and BM aspiration • During 3 years of obinutuzumab maintenance: blood every 6 months and BM aspiration at the end of the 3 years • During 3 years of obinutuzumab maintenance “on-demand” (only for informative MRD at baseline) blood every 3 months • At the end of the “on-demand” maintenance or at premature discontinuation treatment: blood and BM aspiration
Statistical consideration	
The primary endpoint of this phase II study is the MRD in bone marrow according to EU MCL network guidelines after the 4 cycles or at treatment discontinuation whatever reason, of GA-DHAP.
 
Analysis sets
 
The Efficacy set will include all patients having signed their informed consent, received at least one dose of the IMP and with an informative MRD (characterized tumoral clone) in bone marrow (BM) and/or blood at baseline.
 
The Safety set will include all patients having signed their informed consent and received at least one dose of the IMP.
 
The analysis of the primary criterion will be performed on the Efficacy set and also on modified Efficacy Set as sensitivity analysis.
 
Secondary endpoints (including safety endpoints) will be performed on Efficacy and Safety sets.

Sample Size CalculationHypothesis:

We expect to have an increase of 15% of the MRD negativity in bone marrow for patients treated with GA-DHAP.

Based on the interim results of LYMA presented at ASH 2014, the MRD negativity rate was 65% (Legouill, ASH 2014). Nevertheless, in the LYMA study, the MRD has been assessed after 4 cycles of DHAP only for patient that completed the 4 cycles. Therefore this rate does not take into account the rate of patients who progressed on treatment or took R-CHOP because of insufficient response. If we take into account these patients considering them as non responder patients and based on the LYSA/LYSARC experience, then the MRD negativity rate of all patients in the LYMA may be around 55%. Considering that these patients will also be included in the LyMa101 we have to take into account a rate of 55% of MRD negativity instead of 65% in the sample size calculation.

The hypotheses are as follows:

- Experimental treatment will be considered ineffective if the MRD negativity in BM after the 4 cycles or at treatment discontinuation proportion is $\leq 55\%$ (P0)
- Experimental treatment will be considered effective if the MRD negativity in BM after the 4 cycles or at treatment discontinuation proportion $\geq 70\%$ (P1)
- α risk of 0.05 and β of 0.20
- one-sided test

Patients will be considered as MRD positive if the patient has no MRD assessment after the 4 cycles or at treatment discontinuation due to whatever reason.

Sample Size:

A total of 70 patients will be required for this study. Assuming that some included patients will not receive the treatment or will not be informative for MRD in bone marrow and/or blood at baseline, enrollment will be done until 70 patients are evaluable. For this purpose, about 83 patients should be enrolling (15% drop-out).

Among the 70 evaluable patients, if 46 patients or more have a MRD negativity in BM after the 4 cycles or at treatment discontinuation, the treatment will be considered as sufficiently effective and further investigations will have to be foreseen.

Sample size calculation was performed using an exact single-stage phase II design with East 5.4 (A'Hern RP. *Sample size tables for exact single-stage phase II designs*. *Stat Med*. 2001. 20(6):859-66).

Analysis Plan

The primary endpoint of this phase II study is the MRD in bone marrow after the 4 cycles or at treatment discontinuation.

	
Continuous data: will be summarized in tables displaying number of patients, mean, standard deviation, median, range; quartiles will also be presented when considered relevant.
 
Categorical data: will be described in counts and percentages (of non missing data)
 
Response and MRD rates (according to Cheson 1999 or at a molecular level): will be expressed with 90% confidence limits (to be consistent with one sided 5% level of significance) according to Pearson-Clopper method. The number and percent of patients falling into each category of response will be provided.
 
Time to event: will be performed using Kaplan-Meier method. Survival probabilities, median survival and quartiles will be estimated with their 95% CI. Survival curves will be provided.

Safety consideration	
Time of Analysis
 
Given the fact that primary endpoint is prematurely determined in study treatment period, 2 types of analysis will be performed:
 
 • Primary criterion analysis • Final analysis 
Primary criterion analysis:
 
Primary criterion analysis will be performed once all patients included in efficacy set (70 evaluable patients) have completed 4 cycles of treatment or treatment discontinued prior to cycle 4 of the study and will consist of analyzing:
 
 • Primary criterion : MRD rate in bone marrow after the 4 cycles or at treatment discontinuation of GA-DHAP • Treatment exposure • Stem cell collection failure • Secondary safety endpoints 
Final analysis:
 
All analyses will be performed when all included patients will have performed the end of treatment visit (end of maintenance “on demand” period or treatment discontinued from the study).
 
 • AE of grade 3-5 (CTCAE – v 4.03) regardless the relationship to IMP occurring from the date of informed consent signature, and up to 28 days after last treatment administration, will be recorded on the AE pages of eCRF. • Some adverse events which are attributable to the ASCT procedure only and not to the study drug are not to be entered in the eCRF (listed in section 14.2). • Any grade for AESI will be collected from ICF signature and until 28 days after last treatment administration regardless the relationship to IMP • All events that meet one or more criteria of seriousness, regardless the relationship to IMP, occurring from the date of the informed consent signature, during treatment administration period and up to 28 days after last drug administration, will be reported as SAE.

	
A SAE that occurs after this time, including follow up period, will be reported if considered related to IMP.
 
In a case of SAE the Investigator must immediately (within 24 hours):
 
SEND the SAE pages to LYSARC Pharmacovigilance department: [contact] OR EMAIL TO [contact]
 
Pregnancy and suspected pregnancy will be reported on Pregnancy Form to LYSARC PV from the date of informed consent signature and up to 28 days after the last study drug administration.

Independent Data Monitoring Committee	
This trial is designed to allow premature termination or modification of the protocol for safety concerns based on an Independent Data Monitoring Committee (IDMC). Safety variables based on NCI-CTCAE v4.0 and described below will be followed by the LYSARC and a IDMC review will be planned when the rate of these AE is greater than expected.
 
Safety variables assessed and planning of a IDMC meeting when:
 
 - during the induction : IRR grade 4, identified as AESI, $\geq 10\%$ or infections grade 3-4 $\geq 25\%$ or opportunistic infections $\geq 5\%$ - during the ASCT : toxic deaths $\geq 5\%$ - during the maintenance : infections grade 3-4 $\geq 10\%$ - throughout the study : SAE $\geq 60\%$, all death not related to the disease will be analyzed by LYSARC pharmacovigilance department that could induced a safety review
Planned Timelines	
Date first patient included: November2016
 
Duration of enrollment: about 2 years
 
Planned date last patient included: September 2018
 
Planned date last patient last visit: Q1 2025
 
Primary criterion analysis: Q1 2019.
 
Final analysis: Q1 2025

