11.4 PET scan interpretation

Local analysis of the PETs should be done according to Lugano recommandations for baseline PET. Additional quantitative datas (listed in the CRF) will be registered.

Local analysis of the PETs should be done according to Lugano recommandations using Deauville criteria (appendix 9-10) for PET realized before and after ASCT. Additional quantitative data (listed in the eCRF) will be registered.

A central review of the 3 FDG-PET scan should be organized for this study with sending CD.

For each patient when applicable, the following data and images will be reviewed by a panel of PET experts:

- Baseline FDG-PET (PET0)
- FDG-PET realised after Induction (before ASCT)
- FDG-PET realised after ASCT (before maintenance)

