20.10 Appendix 10: Deauville criteria for PET analysis

Deauville criteria is a scoring system and it will be used for intermediate evaluation of PET realized before and after ASCT.

We will use a 5 points scale (adapted from the Deauville workshop in Leukemia & Lymphoma, August 2009; 50(8): 1257–1260), with new modifications (mainly 4 and 5 scales).

It includes visual and quantitative analysis.

1. No uptake.
2. Uptake < mediastinum.
3. Uptake > mediastinum but < liver.
4. Uptake moderately more than liver uptake, at any site.
5. Markedly increased uptake at any site and/or new sites of disease.

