##### PET result after 3 years of maintenance

PET result after 3 years of maintenance will be evaluated. Assessment of PET will be based on Lugano 2014 criteria (according to Cheson & Al. J. Clinic Oncol 2015). See Appendix C (Reponse criteria for lymphoma – Lugano classification).

This endpoint will be analyzed on efficacy set (ES) and on safety set (SS).

#### 3.2.2.3 Secondary efficacy endpoint 3

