### 5.7.4 Response rate

Table 5.7-6 Response according to Cheson 99 – Efficacy Set

		Evaluation after 3 years of maintenance N=XX	End of treatment N=XX
Response (Cheson 99)			
Complete Metabolic Response		XX (XX.X%)	XX (XX.X%)
Partial Metabolic Response		XX (XX.X%)	XX (XX.X%)
No Metabolic Response		XX (XX.X%)	XX (XX.X%)
Progressive Metabolic Disease		XX (XX.X%)	XX (XX.X%)
Not Evaluated		XX (XX.X%)	XX (XX.X%)
Overall Response Rate (ORR)			
Patients with ORR		XX (XX.X%)	XX (XX.X%)
IC 95%		[XX.X% - XX.X%]	[XX.X% - XX.X%]
Overall Response Rate* (ORR)			
Patients with ORR		XX (XX.X%)	XX (XX.X%)
IC 95%		[XX.X% - XX.X%]	[XX.X% - XX.X%]

\* Patients who relapsed or died during treatment phase are considered as non-responders even if they were responders before withdrawal.

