## 5.7.5 PET results

**Table 5.7-7 PET scan result – Efficacy Set**

	After Induction N=XX	After ASCT N=XX	After 3 years of maintenance N=XX	End of Treatment N=XX
PET scan				
No	XX (XX.X%)	XX (XX.X%)	XX (XX.X%)	XX (XX.X%)
Yes	XX (XX.X%)	XX (XX.X%)	XX (XX.X%)	XX (XX.X%)
If done, hypermetabolic lesion				
No	XX (XX.X%)	XX (XX.X%)	XX (XX.X%)	XX (XX.X%)
Yes	XX (XX.X%)	XX (XX.X%)	XX (XX.X%)	XX (XX.X%)
If yes, SUV Max tumoral				
N	XX	XX	XX	XX
Missing	XX	XX	XX	XX
Mean (SD)	XX.X (XX.XX)	XX.X (XX.XX)	XX.X (XX.XX)	XX.X (XX.XX)
Median	XX.X	XX.X	XX.X	XX.X
Q1 ; Q3	XX ; XX	XX ; XX	XX ; XX	XX ; XX
Min ; Max	XX ; XX	XX ; XX	XX ; XX	XX ; XX
If yes, localisation				
XXX	XX (XX.X%)	XX (XX.X%)	XX (XX.X%)	XX (XX.X%)
XXX	XX (XX.X%)	XX (XX.X%)	XX (XX.X%)	XX (XX.X%)

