## 7.5 Appendix C: Response Criteria for Lymphoma – Lugano Classification

Bruce D. Cheson, Richard I. Fisher, Sally F. Barrington, Franco Cavalli, Lawrence H. Schwartz, Emanuele Zucca, and T. Andrew Lister. *J Clin Oncol* 2014;32(27):3059-68.

Revised Criteria for Response Assessment		
Response and Site	PET-CT-Based Response	CT-Based Response
Complete	Complete metabolic response	Complete radiologic response (all of the following)
Lymph nodes and extralymphatic sites	Score 1, 2, or 3 with or without a residual mass on 5 Point Scale†  It is recognized that in Waldeyer's ring or extranodal sites with high physiologic uptake or with activation within spleen or marrow (eg, with chemotherapy or myeloid colony-stimulating factors), uptake may be greater than normal mediastinum and/or liver. In this circumstance, complete metabolic response may be inferred if uptake at sites of initial involvement is no greater than surrounding normal tissue even if the tissue has high physiologic uptake	Target nodes/nodal masses must regress to $\leq 1.5$ cm in LD  No extralymphatic sites of disease
Nonmeasured lesion	Not applicable	Not applicable
Organ enlargement	Not applicable	Rgress to normal
New lesions	None	None
Bone marrow	No evidence of FDG-avid disease in marrow	Normal by morphology; if indeterminate, IHC negative

Partial	Partial metabolic response	Partial remission (all of the following)
Lymph nodes and extralymphatic sites	Score 4 or 5† with reduced uptake compared with baseline and residual mass(es) of any size At interim, these findings suggest responding disease At end of treatment, these findings indicate residual disease	≥ 50% decrease in SPD of up to 6 target measurable nodes and extranodal sites When a lesion is too small to measure on CT, assign 5 mm x 5 mm as the default value When no longer visible, 0 x 0 mm For a node > 5 mm x 5 mm, but smaller than normal, use actual measurement for calculation
Nonmeasured lesion	Not applicable	Absent/normal, regressed, but no increase
Organ enlargement	Not applicable	Spleen must have regressed by > 50% in length beyond normal
New lesions	None	None

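### After induction and after ASCT, no SAP table gives the Lugano/Deauville PET result that the protocol has read; from year 3, metabolic categories appear only under a Cheson 99 title

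*Protocol*

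**What the plan says.** **Objectives.** The synopsis, Protocol 6.2 and SAP 3.1.2 list two PET objectives among the secondary objectives: "MRD plus in terms of FDG-PET before and after ASCT", and "To evaluate PET results after 3 years of maintenance". Only the second has a formally defined endpoint (Protocol 15.1.2.1; SAP 3.2.2.2), on the Efficacy Set and the Safety Set, where "Assessment of PET will be based on Lugano 2014 criteria".

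**Reading rules.** Protocol 11.4 states: "Local analysis of the PETs should be done according to Lugano recommandations using Deauville criteria (appendix 9-10) for PET realized before and after ASCT". It also plans a central expert review of the baseline, post-induction and post-ASCT scans. Protocol 9.6 and 9.7 name Lugano 2014 beside Cheson 1999 for disease response at the two ASCT visits, and Protocol 9.8 names Lugano 2014 for the year-3 PET. In Protocol Appendix 10, Deauville score 3 is "Uptake > mediastinum but < liver". In Protocol Appendix 9 and SAP Appendix C, complete metabolic response is "Score 1, 2, or 3 with or without a residual mass on 5 Point Scale".

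**Outputs.** SAP 5.7.5 has two PET tables with the same layout, one per analysis set, with columns after induction, after ASCT, after 3 years and at end of treatment. The result row is "If done, hypermetabolic lesion", answered No or Yes. For Yes, SUVmax and localisation follow. SAP 5.7.4 has two response tables, the first titled "Response according to Cheson 99 – Efficacy Set" and the second its Safety Set copy. They cover year 3 and end of treatment only, and their rows are complete, partial, no and progressive metabolic response.

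**The concern.** The protocol pays for a standard five-point reading of the scans around transplant, with expert review, and the SAP then tabulates something else. A lesion seen or not seen is not a Lugano result. If the shells are followed as written, the report cannot say how many patients were in complete metabolic response after GA-DHAP or after ASCT, and its PET figures cannot be set beside results that use Lugano classes. Because the row has no stated threshold, what it counts may also differ between readers.

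From year 3 the difficulty is different. Metabolic categories are tabulated, but under the name of a CT-based system that does not contain them. Two separate secondary endpoints, response by Cheson 99 and PET by Lugano 2014, then share one set of rows, and a reader cannot tell which is being reported.

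**Working it through.** The plan states no figure for PET, so there is none to reproduce. Its one design calculation concerns bone marrow MRD (70 evaluable patients, at least 46 negative). That reproduces, with exact one-sided alpha 0.0452 and power 0.8201, and nothing here touches it. The check sets criteria against table shells.

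**1. After induction and after ASCT**

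- Required: a Lugano/Deauville reading (Protocol 9.6, 9.7, 11.4 and Appendix 10).
- Tabulated: PET done, lesion No/Yes, SUVmax, site (SAP 5.7.5).
- Elsewhere in the SAP: the response tables in 5.7.4 have no column for either time point.
- Result: no Deauville or Lugano output exists for these scans.

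The score cannot be recovered from what is shown. Deauville compares uptake with mediastinum and liver, whereas the table gives tumour SUVmax with no reference value, and only for scans answered Yes.

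**2. What a Yes means**

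- Score 3 is uptake above mediastinum and below liver.
- Scores 1 to 3 are a complete metabolic response.
- Neither document defines a hypermetabolic lesion.
- Result: a score 3 focus may be entered as Yes, because it exceeds mediastinal uptake, or as No, because it is below liver and is a complete response under Lugano. The plan does not decide.

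**3. Size of any shift**

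If k score 3 scans among n scans performed are entered as Yes, the lesion rate rises by 100 × k/n points compared with a split at scores 1–3 against 4–5. The documents give no Deauville 3 rate, so k is an assumption. Taking n = 70, as if every Efficacy Set patient were scanned:

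- k = 0: 0 points
- k = 1: 100 × 1/70 = 1.4 points
- k = 4: 100 × 4/70 = 5.7 points
- k = 7: 100 × 7/70 = 10.0 points
- k = 14: 100 × 14/70 = 20.0 points

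The row is conditional on a scan having been done, so n may be below 70 and each scan would then weigh more.

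**4. Year 3 and end of treatment**

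- Cheson 99 categories in Protocol Appendix 8: CR, CRu, PR, SD, PD (and relapse).
- Rows in SAP 5.7.4: metabolic categories, as in the PET column of SAP Appendix C.
- The SAP uses the Cheson 99 categories correctly in 5.8, for response after treatment of progression.
- For the end-of-treatment visit, Protocol 9.9 lists CT and a Cheson 1999 evaluation and does not name PET, yet the 5.7.4 rows for that visit are metabolic.
- Result: either the title or the rows of the 5.7.4 tables are wrong, and the document does not show which.

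**The case against.** The strongest reply is that the only formally defined PET endpoint is at year 3, and metabolic categories are tabulated at year 3 on the two analysis sets that the endpoint names. This stands in part. A reader of SAP 5.7.5 alone might infer that the SAP nowhere reports PET by Lugano; the 5.7.4 tables mean the documents do not support that reading. They do not settle the matter either, because they carry a Cheson 99 title and omit both ASCT time points.

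A reader might also infer that every Deauville 3 scan will be counted as positive, and that the PET-negative rate is therefore understated by some definite amount, say 5 to 15 points. The documents do not support this. The SAP has no PET-positive label and does not say that any raised uptake counts, and a reader trained on Lugano could record No for score 3. The term may be an eCRF field defined elsewhere; the eCRF is not among the documents. The lower bound of the effect is zero.

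Finally, the consequence is limited. The primary endpoint is bone marrow MRD, Protocol 9.11 bases progression on CT rather than PET, and no hypothesis or decision rule rests on PET. That is right, and it bears on priority. It does not explain why a required reading around transplant has no output.

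**Conclusion.** The point holds for the scans after induction and after ASCT. They serve a secondary objective and the protocol has them read by Lugano/Deauville, but the SAP as written produces no Lugano or Deauville result for them. This rests on the text alone and needs no assumption about rates.

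That a Deauville 3 scan may be tabulated as a lesion is a possibility created by an undefined term. Its size is unknown and may be zero; the 1.4 points per scan assumes 70 scans.

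At year 3 and end of treatment the fault is one of labelling. Metabolic categories are present under the wrong system's name, so neither the Cheson 99 endpoint nor the Lugano endpoint is cleanly reported. The primary analysis is unaffected. The change is worth making because it is cheap and lets the trial answer objectives it already states.

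**What to change.** In both PET tables of SAP 5.7.5 (Efficacy Set and Safety Set):

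- Add Deauville score 1 to 5 and Lugano metabolic response class after induction, after ASCT and after 3 years.
- Give the complete metabolic response rate (score 1–3) with 90% Clopper-Pearson limits, the level and method that Protocol 15.4 and SAP 4.5.1 set for response rates.
- Keep the lesion, SUVmax and site rows as description only.
- State for each time point whether the central or the local read is used. The central review in Protocol 11.4 covers baseline, post-induction and post-ASCT and does not list the year-3 scan.

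In both response tables of SAP 5.7.4, replace the metabolic labels with CR, CRu, PR, SD and PD, and report the metabolic categories in the PET section.

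The cost is table shells and a sentence or two in the SAP, with no new scans. Deauville is named explicitly only for the scans before and after ASCT; at year 3 the score follows from the Lugano 2014 criteria in Protocol 9.8 and 15.1.2.1. Scores not held in the eCRF would come from existing PET reads or, for the scans it covers, the planned central review.
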